2.3.6 Summary and gaps

In conclusion, various studies have applied SCGs for MCI screening among older adults, revealing significant differences in game performance between those with MCI and their healthy counterparts However, despite these promising findings, several gaps and areas for further study remain evident. Notably, the correlations between the game metrics and the traditional cognitive scores found were not robust, and demographic variables were often overlooked in these analyses, limiting the concurrent validity of the used game-based screenings. This oversight

suggests a need for more comprehensive research to understand better how demographic factors might influence the outcomes of game-based cognitive screenings.

The variability in game scenarios, dependence of the results and usability on the specific games and their availability, and small sample sizes also limit the generalizability of these findings, highlighting a clear need for further research. Future studies should also focus on integrating demographic variables, employing larger sample sizes, and exploring a wider variety of game types to enhance validity and usefulness of SCGs. Furthermore, the availability of SCGs used in previous studies is limited, and they are not accessible for older adults and clinicians to use in everyday life or clinical settings.

Research should also examine the psychological impact of game-based screenings, such as state anxiety, compared to traditional screenings. Understanding the levels of anxiety induced by different types of screenings can help improve the design and implementation of SCGs, making them more user-friendly and less intimidating for older adults. This could broaden the acceptance and effectiveness of these innovative tools in MCI screening.

Moreover, there is a need to explore the integration of real-life scenarios into SCGs, such as Activities of Daily Living (ADL) and instrumental ADL (iADL), to provide a more realistic assessment of cognitive abilities. Custom-designed games that mimic real-life activities have shown promising results, and further research in this area could enhance the ecological validity of SCGs.

In conclusion, while SCGs hold great promise for MCI screening, addressing these gaps through comprehensive research will be essential for establishing their reliability, validity, generalizability and widespread applicability.

3. Method

3.1 Study design

This study is an observational cross-sectional study. Since the G3 in this study has never been used for screening cognitive status, its validity as an indicator for MCI and its diagnostic accuracy are unknown. Given the novelty and untested nature of G3, a cross-sectional design is chosen for its cost-effectiveness and time efficiency, making it suitable for a feasibility study to explore the game's validity, usability, and diagnostic accuracy. Moreover, recruiting a large sample size for a longitudinal or repeated measures study and undertaking extensive data collection would be unethical for a tool whose usability, validity, and diagnostic accuracy have not been previously assessed. This is particularly relevant for older adults with cognitive impairments, who are a vulnerable population. Therefore, a cross-sectional study is the best approach for the first steps of research in the area using the G3.

3.2 Participants

3.2.1 Inclusion criteria

- Older adults who are aged 65 and above with typical cognition or MCI as reported by themselves, or a health care professional.
- Older adults participating in this study must have MoCA score of 18 or higher.
- Older adults participating in the study must have functional vision and hearing, with or without aids such as glasses or hearing aids that enable them to interact with the game and comprehend the instructions. As part of the study recruitment activities, the researcher will explain the tasks required and discuss the vision and hearing demands.

- Older adults participating in the study must be capable of communicating and comprehending assessments, instructions, and simple sentences in English, as communication and comprehension is essential for interacting effectively with game components and the researcher. To assess their communication, reading, and comprehension skills, the researcher will provide participants with a few sentences in English related to the game content. Participants will be asked to read these sentences aloud and explain the meaning of the sentence to confirm their ability to read and understand the content.
- Older adults participating in the study must have adequate upper extremity function to play the game, using a mouse and do paper-and-pencil based measurements, using a pencil. During the study's introduction and training part of the game, potential participants can report any physical limitations. The researcher will also screen for these issues.

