1.1 Background

As global life expectancy continues to rise, the number of older adults also increase (1). The global population of individuals aged 65 and older is expected to surge from 761 million in 2021 to 1.6 billion by the year 2050, highlighting a significant demographic shift (2). The aging trend leads to a significant rise in the prevalence of cognitive impairments, notably Mild Cognitive Impairment (MCI) and dementia. Dementia, is a progressive syndrome that damages the brain, leading to a decline in cognitive function, behaviour, and ability to perform Activities of Daily Livings (ADL) beyond what is typically expected from normal aging (3). Dementia has significant physical, psychological, social and economic impacts on individuals living with this condition, as well as on their care givers, families and society (3). Dementia affects nearly half a million Canadians aged 65 and older (4). Given dementia's status as a significant cause of disability and dependency among older adults, and as the 7th leading cause of death globally, the World Health Organization has prioritized dementia as a public health concern (3). MCI often represents a critical transitional stage between normal aging and dementia (5). Unlike normal aging, which involves gradual cognitive decline without significant impact on daily living activities, MCI causes notable reductions in cognitive abilities, particularly affecting instrumental Activities of Daily living (iADL) (6). Importantly, 10% to 15% of individuals with MCI annually progress to dementia (7)- significantly higher than the 1% to 2% incidence annually in the general population, and up to 18% revert to normal cognitive status (8). Early detection MCI is consistent with the goal of high-quality health care. It facilitates timely access to information and treatments (9,10). It also allows for the modification of risk factors like smoking, physical inactivity, and social isolation, potentially delaying disease progression (11).

Additionally, it assists in identifying potential participants for research, essential for evaluating new treatments (9,12). Early detection also allows the patients to discuss their situation with clinicians and family members, insights into prognosis, care preferences, and future financial and living arrangements plans (9,10).

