Subsequent studies have broadened the symptoms of MCI to include other cognitive domains, leading to the development of the Petersen Criteria (62). Petersen criteria are characterized by a cognitive complaint, preferably confirmed by an informant, intact global cognition, unimpaired ADL, and absence of dementia, without significant disruption of iADL (62). However, subtle challenges in iADL might be evident (63). The Diagnostic and Statistical Manual of Mental Disorders 5th Edition (DSM-V) also characterizes MCI as a "mild neurocognitive disorder." It requires both subjective and objective cognitive decline compared to the prior level of cognitive abilities but is not defined as dementia or other psychological disorders (64). The prevalence of MCI varies widely, ranging from 0.5% to 41.8% (65), with an overall prevalence of 19.7% in the world (66). Risk increases with age, and men appear to be at higher risk than women (67). Additionally, lower educational level, vascular risk factors (e.g., diabetes and hypertension), Apolipoprotein E (APOE) e4 genotype, vitamin D deficiency, sleepdisordered breathing, and prior critical illness (e.g., sepsis) are other risk factors for MCI (68,69). Classification of MCI is challenging due to its heterogeneous nature. However, it could be classified based on either etiology or the existence of memory impairment (61). Based on etiology MCI is classified into 1. MCI associated with Alzheimer's Disease (AD) which is associated mostly with memory decline. However, it might affect other cognitive domains as well (70); 2. Vascular MCI (VMCI) is related to issues with blood vessels in the brain, affecting multiple cognitive functions (71); 3. MCI caused by Parkinson's Disease (PD-MCI) represents a transitional state between normal cognition and dementia in Parkinson's disease, affecting either memory or other cognitive domains or even both memory and other cognitive domains (72). MCI is also classified based on the presence of memory impairment. It is divided into amnestic

(aMCI), involving memory decline with or without other cognitive issues, and non-amnestic (non-aMCI), marked by impairments in cognitive areas other than memory (61).

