2.2.5 MCI diagnosis

Early detection of MCI is beneficial for several reasons. It facilitates timely access to information and treatments (9). It also allows for the modification of risk factors like smoking, physical inactivity, and social isolation, potentially delaying disease progression (11). Additionally, it assists in identifying potential participants for research, essential for evaluating new treatments (9,12). Early detection enables patients to converse with clinicians and family members about their condition, providing insights into prognosis, care preferences, and future financial planning. (9,10). However, diagnosing MCI is challenging and cannot be confirmed by a single test. People who are concerned about their cognitive abilities should be thoroughly assessed through a detailed history and clinical examination. This evaluation should emphasize cognitive capabilities, everyday functional status, current medications, and any neurological or psychiatric conditions. It is also important to conduct laboratory tests (13). The main aims are to distinguish MCI from typical aging or dementia and to detect any reversible factors contributing to MCI, such as depression, side effects from medications, thyroid issues, or deficiencies in vitamin B12 or folate (13). Cognitive function is assessed using traditional cognitive tests such as the Montreal Cognitive Assessment (MoCA), Mini-Mental State Exam (MMSE), Saint Louis University Mental Status (SLUMS), and Quick mild cognitive impairment (Quickmci). The MMSE is one of the most used cognitive tests measure several cognitive abilities in 5 to 10 minutes. MMSE was shown to have a good test-retest reliability (0.80-0.95) (102-104). MMSE is also concurrently valid (103,104); however, it is not sensitive enough to detect MCI. Sensitivity and specificity have been recorded inconsistently ranging from 13% to 97%, and 60% to 100% respectively, considering this variation in accuracy, MMSE is less reliable for MCI detection, specifically at an early stage (105–108).

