3.3 Sample size

The correlational analysis was selected for determining the sample size of this study. The main reason for that is that the diagnostic accuracy and validity testing are the primary objectives of this project. Calculating the sample size based on correlational analysis offers a robust approach

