to examining the relationship between game performance and cognitive status, requiring a moderate number of participants. Thus, this study, designed with a statistical power of 0.8, an alpha level of 0.05, and a medium effect size of 0.7, requires a minimum sample size of 58 participants. Twenty-nine older adults (65 and above) who meet the diagnostic criteria for MCI, and 29 older adults with typical cognition will be eligible to participate in the study. Other reasons for justifying the sample size include: 1) The statistical analyses to answer questions that aim to compare two conditions, or two groups requires a smaller sample size; and this small sample size is insufficient to justify correlational analysis. 2) the "Events Per Variable" (EPV) rule is often used in statistical modeling, particularly in logistic regression, to determine the minimum sample size needed to ensure reliable and valid results. The general rule is to have at least 10 events (outcomes of interest) for each predictor variable (151). Therefore, using regression analysis to explore the six associated factors (game performance, age, sex, educational level, tech savviness, and living status) with the presence of MCI would necessitate 60 events (instances of the outcome of interest). Assuming an equal distribution of events and non-events, at least 120 participants would be needed in total to achieve 60 events, ensuring that each predictor variable is adequately supported by the data and enhancing the reliability of the statistical model. However, for a feasibility study involving a brand-new, untested test, it is not ethical to recruit a large sample size and burden vulnerable older adults with participation. Besides, at this point of the study, it is not known how many independent variables will be included in the model and that depends on the results of the factorial analysis that precedes the logistic model. Therefore, I aim to treat the research about the associated factors with the presence of MCI (RQ4) as a pilot to gather preliminary data. This approach can help refine the research design and hypotheses, and the results can be used to justify the need for a larger study

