3.9 Data analysis

To explore the difference between game performance in PwMCI and healthy comparison group (RQ1), the Unpaired t-test or Mann-Whitney U test as appropriate (155), with an α level of 0.05, will be applied. If the mean difference is statistically significant, it indicates that G3 can classified older adults with typical cognition and older adults with MCI based on their game performance. In addition, a two-way factorial multiple analysis of covariance (MANCOVA) (155) will be performed to compare the effects of demographics as covariates on the differences between groups.

To explore the association between the game performance and traditional cognitive tests, including MoCA and Qmci (RQ2), correlational analysis (155) between the game metrics and the scores of each traditional cognitive tests, including total score sub-scores such as memory and executive functions will be conducted. If the correlation coefficient (r) is positive closer to one, it means that the concurrent validity of G3 as an MCI screening tool is good.

To investigate the diagnostic accuracy of the game-based screening (RQ3), formulas will be used as follows:

Sensitivity: Proportion of true positives correctly identified = $\frac{TP}{TP+FN}$

Specificity: Proportion of true negatives correctly identified = $\frac{TN}{TN+FP}$

Accuracy: Overall correctness of the testx = $\frac{\text{TP+TN}}{\text{Total Population}}$

Where TP: True Positives, TN: True Negatives, FN: False Negatives, FP: False Positives (155). Additionally, the interpretation of the Receiver Operating Characteristic (ROC) and Area Under the Curve (AUC) will be used for examination of diagnostic accuracy (155). The ROC curve is a graphical plot that illustrates the diagnostic ability of a binary classifier system as its discrimination threshold is varied. The curve is created by plotting the True Positive Rate (TPR) against the False Positive Rate (FPR) at various threshold settings (155).

The following steps will be used to calculate the ROC curve:

Firstly, the True Positive Rate (TPR), also known as sensitivity or recall, will be determined using the formula:

$$TPR = \frac{TP}{TP + FN}$$

Secondly, the False Positive Rate (FPR), also known as (1 - specificity), will be determined using the formula:

$$FPR = \frac{FP}{FP+TN}$$

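### Group status may rest on self-report (3.2.1) or on unnamed diagnostic criteria (3.3), and the reference standard for RQ3 is not stated

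*Protocol*

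**What the plan says.** - Protocol 3.2.1 defines who enters, and as what: "Older adults who are aged 65 and above with typical cognition or MCI as reported by themselves, or a health care professional". The two sources are joined by an "or"-type alternative, so self-report alone suffices. The next criterion, MoCA 18 or higher, applies to everyone.
- Protocol 3.3 describes the MCI group as 29 people "who meet the diagnostic criteria for MCI, and 29 older adults with typical cognition will be eligible to participate in the study". Section 3 names no criteria, no assessor and no confirmation step.
- Protocol 3.3 also states that "the diagnostic accuracy and validity testing are the primary objectives of this project".
- Protocol 3.6 defines cognitive status as MoCA and Qmci scores for RQ2 and as a 1/0 MCI code for RQ4. It gives no rule for setting the code.
- Protocol 3.7 has the researcher screen against the 3.2 criteria. For group status this means the reported status again.
- Protocol 3.9: "To investigate the diagnostic accuracy of the game-based screening (RQ3), formulas will be used as follows". The formulas for sensitivity, specificity, accuracy and the ROC curve follow. None says what makes a case truly MCI.
- The protocol's own review asks for more than a report. Section 2.2.5 says that people worried about their cognition "should be thoroughly assessed through a detailed history and clinical examination". Section 2.2.1 says of the DSM-V definition: "It requires both subjective and objective cognitive decline compared to the prior level of cognitive abilities".
- Protocol 3.11 lists misclassification as a limitation.

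**The concern.** An accuracy study is defined by what the index test is compared with. Here 3.2.1 and 3.3 describe the same group in two ways that need not coincide, and 3.9 does not choose between them. If 3.2.1 is followed, the study measures how well G3 agrees with reported status. The wording of 3.3 would let the same numbers be presented as accuracy against diagnosed MCI. RQ1 compares the two groups, RQ4 models the 1/0 code, and RQ3 needs a true status for every participant, so one undefined label runs through three of the six research questions. If the source of each label is not written down at enrolment, no later analysis can recover it.

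**Working it through.** **1. The passages side by side**

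| Section | What decides MCI status |
|---|---|
| 3.2.1 | Own report or a professional's report |
| 3.3 | Diagnostic criteria, not named |
| 3.6 | 1/0 code, no rule |
| 3.7, 3.8 | No step that assigns or verifies group |
| 3.9 (RQ3) | Not stated |

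Three readings fit some of this text:
- *Reported status.* This fits 3.2.1 and conflicts with 3.3.
- *A diagnosis already received and then reported.* This would fit both, but the label is still unverified, and no rule covers a participant and a professional who disagree.
- *A test-derived label.* Section 3.8 gives MoCA and Qmci to everyone to assess cognitive status, 2.2.5 quotes cut-offs (MoCA 26, Qmci below 62), and 3.6 puts the 1/0 code beside those scores. No Methods text applies the cut-offs.

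The third reading would also need a choice between the tests. With the 2.2.5 figures (MoCA sensitivity 89%, specificity 79%; Qmci 90%, 87%), half the sample with MCI, and the tests assumed independent given true status, they disagree in

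0.5 × (0.89×0.10 + 0.11×0.90) + 0.5 × (0.79×0.13 + 0.21×0.87) = 0.237,

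which is 0.237 × 58 ≈ 14 participants.

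**2. What label error does to RQ3**

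The plan gives no figure for label error, so there is none to reproduce. Let f be the share of the typical group who have MCI, g the share of the MCI group who do not, and A the true AUC (0.85 assumed). If mislabelled people play like their true group, then

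apparent AUC = 0.5 + (A − 0.5)(1 − f − g).

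The mean difference and Youden's index shrink by the same factor.

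*Mild case.* Section 2.2.1 reports MCI "with an overall prevalence of 19.7% in the world". If a quarter of MCI among volunteers goes unreported (assumed),

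f = 0.197×0.25 / (0.803 + 0.197×0.25) = 0.049/0.852 = 0.058, or 1.7 of 29.

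With g = 0, AUC = 0.5 + 0.35×0.942 = 0.83.

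*10% mislabelled in each group (assumed).* AUC = 0.5 + 0.35×0.80 = 0.78. On the 3.9 scale this moves from excellent to acceptable.

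**3. Errors that track the game score**

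Simulation: 400,000 per group, normal scores, A = 0.85, 10% mislabelled in each group. The tendency to be mislabelled is correlated with G3 score, so that poor players who are typical are labelled MCI and good players with MCI are labelled typical.

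| Correlation | Apparent AUC |
|---|---|
| 0 | 0.78 |
| 0.3 | 0.83 |
| 0.5 | 0.86 |

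The bias is usually downward, but it can cancel or turn slightly upward.

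**The case against.** The best defence has four parts.

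- *The conflict is soft.* MCI is a clinical term, so a reported MCI may well be a reported diagnosis, and 3.7 recruits through hospitals and memory clinics. This is plausible, but the protocol does not say it, and 3.2.1 equally admits someone with no diagnosis.
- *MoCA and Qmci may be the intended standard.* The MoCA floor of 18 equals the dementia cut-off quoted in 2.2.5, which suggests that the tests were in mind. That keeps the reading open; it does not state it.
- *The rule for the 1/0 code may sit in an analysis plan that is not shown.* It may, and the derivation alone would not be a finding. The clash between 3.2.1 and 3.3, however, is in the protocol and concerns who is enrolled.
- *This is a feasibility study, and 3.11 concedes misclassification.* That lowers the severity. It does not settle which label RQ3 uses, and 3.11 itself gives diagnostic accuracy as a focus of the study.

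Two stronger readings are tempting. A reader might infer that RQ3 has no reference standard at all; the text supports only that none is stated, since the enrolled label could serve as a weak implicit one. A reader might also combine the whole 19.7% prevalence with the 1.1 statement that "up to 18% revert to normal cognitive status" and get a factor of 1 − 0.197 − 0.18 = 0.62, hence an AUC of 0.72. The documents do not support that as a realistic case. It needs all MCI among volunteers to go unreported, although the same volunteers supply self-reported cases. It also needs the maximum reversion to apply to all 29 MCI participants, and a worldwide prevalence to hold among people who call themselves typical.

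**Conclusion.** The concern holds in this form: 3.2.1 and 3.3 disagree on what puts a participant in the MCI group, the Methods apply no criteria, and the reference standard for RQ3 is not stated. The finding is textual and does not depend on any error rate. The size is illustrative only: with an assumed true AUC of 0.85, the apparent value is 0.83 or 0.78 for the two error patterns unrelated to G3, and up to 0.86 when errors track the score at correlation 0.5. The true rates, and the number of participants with a professional diagnosis, are unknown. It would be wrong to conclude that the labels will be badly wrong or that accuracy will be inflated; the documents show neither. This should be fixed before enrolment, because the label source has to be captured then.

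**What to change.** 1. Reconcile 3.2.1, 3.3, 3.6 and 3.9 into one stated reference standard, independent of G3, used for RQ1, RQ3 and RQ4. Give a single rule that places each participant in exactly one group, including when reports conflict. If MoCA/Qmci cut-offs are chosen, acknowledge that the RQ2 comparators then also define the groups.
2. If self-report remains sufficient, delete the claim in 3.3 that the MCI group meets diagnostic criteria, and describe RQ3 as accuracy against reported status.
3. Record at enrolment where each label comes from: own report without a diagnosis, own report of a diagnosis, or a professional's report.
4. Keep all eligible participants in the main analysis. Repeat RQ1, RQ3 and RQ4 as a sensitivity analysis with the MCI group limited to those with a professional diagnosis (reported or documented), against all typical participants. This does not require professionally labelled controls, who may not exist.
5. Optionally, repeat without participants whose label disagrees with both MoCA and Qmci. At the 2.2.5 accuracies this could remove up to 29×0.13 + 29×0.10 = 6.7 correctly labelled people, and it tends to favour G3.

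Cost: rewording of four sections, one recorded field and one sensitivity analysis, with no new tests. The price is a smaller subset in that analysis and a more modest accuracy claim. Clinician confirmation of every MCI case is an option and not needed for this fix. It would require letters or record access, probably consent and ethics changes, within the nine months of data collection in 3.12 and with no budget line in 3.13.
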